7. PLANNED ANALYSIS

Safety analysis (refer to [Section 7.8](#)) will be performed by [REDACTED] and will be presented in Sections 15.1 to 15.4 of the CTR and in Appendix 16.2 and 16.1.13.1.

PK evaluation will be performed by [REDACTED] and monitored by the [REDACTED]
[REDACTED] and the descriptive

statistics of PK endpoints and plasma concentrations will be presented in Section 15.6 of the CTR. Inferential statistical analyses of PK endpoints will not be applied in this trial due to the premature discontinuation.

The format of the listings and tables will follow BI standards (see BI-KMED-BDS-HTG-0045 (7)) with the exception of those generated for PK evaluations following BI standards for PK/PD analysis (8).

The individual values of all subjects will be listed, sorted by treatment, subject number and visit. The listings of PK and other than PK will be included in Appendices 16.1.13.5 and 16.2 of the CTR, respectively.

For end-of-text tables, the set of summary statistics for non-PK parameters is:

N	number non-missing observations
Mean	arithmetic mean
SD	standard deviation
Min	minimum
Median	median
Max	maximum

For analyte concentrations, the following descriptive statistics will additionally be calculated:

CV	arithmetic coefficient of variation
gMean	geometric mean
gCV	geometric coefficient of variation

For PK parameters, the following descriptive statistics will additionally be calculated:

CV	arithmetic coefficient of variation
gMean	geometric mean
gCV	geometric coefficient of variation
P10	10th percentile
Q1	1st quartile
Q3	3rd quartile
P90	90th percentile

The data format for descriptive statistics of concentrations will be identical to the data format of the respective concentrations. The descriptive statistics of PK parameters will be

calculated using the individual values with the number of decimal places as provided by the evaluation program. Then the individual values as well as the descriptive statistics will be reported with three significant digits in the CTR.

Tabulations of frequencies for categorical data will include all possible categories and will display the number of observations in a category, as well as the percentage (%). Percentages will be rounded to one decimal place and will be based on all subjects in the respective subject set whether they have non-missing values or not. The category 'missing' will be displayed only if there are actually missing values.

Exclusion of PK parameters

The ADS “ADPP” (PK parameters) contains column variables APEXC and APEXCO indicating inclusion/exclusion (APEXC) of a PK parameter and an analysis flag comment (APEXCO). All analyses based on the PKS will include parameters if they are not flagged for exclusion, that is APEXC is equal to “Included”.

Exclusion of PK concentrations

The ADS “ADPC” (PK concentrations per time-point or per time-interval) contains column variables ACEXC and ACEXCO indicating inclusion/exclusion (ACEXC) of a concentration and an analysis flag comment (ACEXCO). Exclusion of a concentration depends on the analysis flag comment ACEXCO. For example, if ACEXCO is set to ‘ALL CALC’, the value will be excluded for all types of analyses based on concentrations. If ACEXCO is set to ‘DESC STATS’ the value will be excluded from descriptive evaluations per planned time point/time interval. If ACEXCO contains the addition ‘TIME VIOLATION’ or ‘TIME DEVIATION’ the value can be used for further analyses based on actual times. If ACEXCO is set to ‘HALF LIFE’, the value will be excluded from half-life calculation (and, as a consequence, any calculation that relies on λ_z) only; the value is included for all other analyses.

Further details are given in *BI-KMED-TMCP-MAN-0014* “Noncompartmental Pharmacokinetic / Pharmacodynamic Analyses of Clinical Studies” (6) and *BI-KMED-TMCP-MAN-0010*: “Description of Analytical Transfer Files and PK/PD Data Files” (9).

7.1 DEMOGRAPHIC AND OTHER BASELINE CHARACTERISTICS

Only descriptive statistics for demographics are planned for this section of the report, based on the TS.

The data will be summarised by treatment and in total.

7.2 CONCOMITANT DISEASES AND MEDICATION

Concomitant diseases will be coded using the latest version of the coding system of the Medical Dictionary for Drug Regulatory Activities (MedDRA). Medications will be coded using the latest version of the World Health Organization Drug Dictionary (WHO-DD). The coding version number will be displayed as a footnote in the respective output.

The diagnoses and medications will be listed. Subjects without any concomitant diagnoses or concomitant therapies should be marked with a “No” in the respective column.

The relevance of the concomitant therapies to the evaluation of PK will be decided no later than at the RPM.

7.3 TREATMENT COMPLIANCE

Section 4.3 of the CTP: *Compliance will be assured by administration of all trial medication in the trial centre under supervision of the investigating physician or a designee. The measured plasma concentrations and/or urinary excretion of trial medication will provide additional confirmation of compliance.*

It is not intended to list the compliance separately. Any deviations from complete intake will be addressed in the RPM (cf. TSAP [Section 6.2](#)) and described in the CTR.

7.4 PRIMARY ENDPOINT

Refer to TSAP [Section 7.8](#) for a description of the analysis of safety and tolerability of BI 894416.

7.5 SECONDARY ENDPOINTS

7.5.1 Key secondary endpoints

This section is not applicable as no key secondary endpoint has been specified in the protocol.

7.5.2 Secondary endpoint

Section 7.3.2 of the CTP: *The secondary endpoints (refer to CTP Section 2.1.3) will be analysed descriptively. Analyses will be performed for the parent drug.*

7.7 EXTENT OF EXPOSURE

The date and time of drug administration will be listed for each subject.

7.8 SAFETY ANALYSIS

All safety analyses will be performed on the TS.

The safety data for treated subjects who failed to complete the study (dropouts or withdrawals) will be reported as far as their data are available. All withdrawals will be documented and the reason for withdrawal recorded.

7.8.1 Adverse Events

AEs will be coded with the most recent version of MedDRA.

The analyses of AEs will be descriptive in nature and will be based on BI standards as presented in “Analysis and Presentation of Adverse Event Data from Clinical Trials – Display Template” [BI-KMED-BDS-HTG-0041] (10) and [BI-KMED-BDS-HTG-0066] (11). All analyses of AEs will be based on the number of subjects with AEs and not on the number of AEs.

The analysis of AEs will be based on the concept of treatment emergent AEs. That means that all AEs will be assigned to ‘screening’, ‘on-treatment’ or ‘follow-up’ phases as defined in [Section 6.1](#). AEs will be analysed based on actual treatments, as defined in [Table 6.1: 1](#).

According to the clinical study protocol, adverse events of special interest (AESI) will be analysed:

Section 5.2.6.1.4 of the CTP: *The following are considered as AESIs:*

- Hepatic injury
A hepatic injury is defined by the following alterations of hepatic laboratory parameters:
 - *An elevation of AST (aspartate transaminase) and/or ALT (alanine transaminase) ≥ 3 -fold ULN combined with an elevation of total bilirubin ≥ 2 -fold ULN measured in the same blood sample, or*
 - *Aminotransferase (ALT, and/or AST) elevations ≥ 10 fold ULN*

These lab findings constitute a hepatic injury alert and the subjects showing these lab abnormalities need to be followed up according to the ‘DILI checklist’ provided in the ISF. In case of clinical symptoms of hepatic injury (icterus, unexplained encephalopathy, unexplained coagulopathy, right upper quadrant abdominal pain, etc.) without lab results (ALT, AST, total bilirubin) available, the Investigator should make sure that these parameters are analysed, if necessary in an unscheduled blood test. Should the results meet the criteria of hepatic injury alert, the procedures described in the DILI checklist should be followed.

According to ICH E3 (12), in addition to Deaths and Serious Adverse Events, 'other significant' AEs need to be listed in the clinical trial report. These will be any non-serious adverse event that led to an action taken with study drug (e.g. discontinuation or dose reduced or interrupted).

An overall summary of AEs will be presented.

The frequency of subjects with AEs will be summarised by treatment, primary system organ class (SOC) and preferred term (PT). Separate tables will be provided for subjects with serious AEs, for subjects with drug-related AEs, for subjects with drug-related serious adverse events and for subjects with AESIs. In addition, the frequency of subjects with AEs will be summarised by treatment, worst intensity, primary system organ class (SOC) and preferred term (PT).

The SOCs and PTs will be sorted by frequency (within SOC). The MedDRA version number will be displayed as a footnote in the respective output.

In addition, frequencies of subjects with non-serious AEs that had an incidence of $> 5\%$ for at least one treatment will be summarised by treatment, primary SOC and PT.

7.8.2 Laboratory data

The analyses of laboratory data will be descriptive in nature and will be based on BI standards [BI-KMED-BDS-HTG-0042] (13).

Laboratory data will be analysed qualitatively via comparison of laboratory data to their reference ranges. Values outside the reference range as well as values defined as possibly clinically significant will be flagged in the data listings.

Clinically relevant findings in laboratory data will be reported as baseline conditions (at screening) or as AEs (during the trial) if judged clinically relevant by the investigator, and will be analysed as such.

It is the investigator's responsibility to decide whether a lab value is clinically significantly abnormal or not (at the RPM at the latest).

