1.4.2 Drug -related risks and safety measures

Potential effects on immune cells

SYK is involved in the function of basophil, mast, neutrophil and dendritic cells. Moreover, SYK is implicated in the development and function of both T cells and B cells. For details refer to the IB [[c03536505](#)].

The risk for healthy volunteers due to effects of BI 894416 on immune cells is expected to be minimal, for the following reasons:

- Inhibition of SYK is not expected to have a negative effect with regards to the immune response of innate immune cells to viral or bacterial infections, due to redundancy in the infection immune response. The key neutrophil and dendritic cell functions most likely will be triggered by alternative pathways.
- Safety and tolerability data of trial 1371-0001 are not suggestive of an increased risk of infectious adverse events, or of any relevant BI 894416-related findings in WBC, differential blood count, immunoglobulins, or lymphocyte subpopulations after single doses up to 70 mg of BI 894416 (see also IB [[c03536505](#)]).
- Due to the reversible mode of action of BI 894416 with regards to SYK inhibition, any potential effect on immune cells are expected to be of transient nature.

Risk mitigation and monitoring: Subjects with a history or diagnosis of immunological disease will be excluded from trial participation (see Section [3.3.3](#)). Adverse events will be monitored for an increase in infectious adverse events. Safety laboratory contains WBC, differential blood count, and C-Reactive Protein.

Tumour biology and carcinogenicity

The SYK pathway has been hypothesized to act as both a tumour suppressor and a tumour promoter in different types of human cancers [[R16-4459](#)]. An increased risk of carcinogenic/metastatic potential in epithelial cancers has been reported in the literature related to SYK knock-out, but not related to SYK inhibition. Allelic deletion of SYK has been associated with breast adenocarcinoma [[R15-4770](#)]. However, there is no evidence that pharmacologic inhibition of SYK will increase carcinogenicity or metastatic risk. Preclinical data with a potent and selective SYK inhibitor, BI 1002494, are in line with an absence of carcinogenic effect due to the inhibition of SYK enzymatic function [[n00243171](#)].

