5.2.3 Safety laboratory parameters

For the assessment of laboratory parameters, blood and urine samples will be collected by the trial site at the times indicated in the Flow Chart after the subjects have fasted for at least 10 h, except 4 h post dosing on Day 1. For retests, at the discretion of the investigator or designee, overnight fasting is not required.

The parameters that will be determined are listed in Tables [5.2.3: 1](#) and [5.2.3: 2](#). Reference ranges will be provided in the ISF.

Manual differential white blood cell count, or urine sediment examinations, will only be performed if there is an abnormality in the automatic blood cell count, and if clinically relevant in the opinion of the investigator, or if the investigator finds an abnormality in the urinalysis.

Proprietary confidential information © 2020 Boehringer Ingelheim International GmbH or one or more of its affiliated companies

Table 5.2.3: 1

Routine laboratory tests

Functional lab group	Test name (comment/abbreviation)	A¹	B¹	C¹
Haematology	Haematocrit Haemoglobin Red Blood Cell Count (RBC) Reticulocytes (relative and absolute) White Blood Cells (WBC) Platelet Count/Thrombocytes (quant) Erythrocyte Sedimentation Rate (ESR)	X X X X X X X	X X X X X X X	X X X X X X X
Automatic WBC differential, (relative)	Neutrophil; eosinophils; basophils; monocytes; lymphocytes	X	X	X
Manual differential WBC (if automatic differential WBC is abnormal)	Polymorphnuclear neutrophils (segs), band neutrophils (stabs), eosinophils, basophils, monocytes, lymphocytes			
Immunoglobulins in serum	IgA IgE IgG IgM	X X X X	-- -- -- --	X X X X
Lymphocyte differentiation (relative)	T cells (CD3+), T helper cells (CD3+CD4+), cytotoxic T cells (CD3+CD8+), B cells (CD19+), natural killer cells (CD16+CD56+CD3-), CD4:CD8 ratio	X	--	X
Coagulation	Activated partial thromboplastin time (aPTT) Prothrombin time (Quick's test and INR) Fibrinogen	X X X	X X X	X X X
Enzymes	AST (Aspartate transaminase)/GOT ALT (Alanine transaminase)/GPT Alkaline phosphatase (AP) Gamma-glutamyl transferase (GGT) Creatine kinase (CK); CK-MB only if CK is elevated Lactate dehydrogenase Lipase Amylase	X X X X X X X X	X X X X -- -- -- --	X X X X X X X X
Hormones	Thyroid Stimulating Hormone (TSH)	X	--	--
Substrates	Plasma glucose Creatinine Total bilirubin Direct bilirubin Total protein C-Reactive Protein Uric acid Total cholesterol Triglycerides	X X X X X X X X	X X X X -- X -- --	X X X X X X X X

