Adverse events will be coded using the Medical Dictionary for Regulatory Activities (MedDRA). Frequency, severity, and causal relationship of AEs will be tabulated by treatment, system organ class and preferred term. SAEs, AESIs (see Section [5.2.6.1](#)) and other significant AEs (according to ICH E3) will be listed separately.

Previous and concomitant therapies will be presented per treatment group without consideration of time intervals and treatment periods.

Laboratory data will be compared to their reference ranges. Values outside the reference range as well as possibly clinically significant values will be highlighted in the listings. Additionally, differences from baseline will be evaluated.

Vital signs or other safety-relevant data will be assessed with regard to possible on-treatment changes from baseline.

The ECG variables QT, HR, QTcF, QTcB, PR, QRS, and RR obtained from the centralised evaluation of 12-lead ECG recordings will be the basis for the derivation of quantitative and categorical ECG endpoints. These endpoints and their analyses will be described in the TSAP.

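### SAP 7.8.2 names no change from baseline for laboratory data, although the protocol promised it. With the differential and lymphocyte subsets given only as percentages, a within-range lymphocyte fall could go unflagged and not be shown as a change.

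*SAP*

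**What the plan says.** **The risk and its monitoring.** Protocol 1.4.2 opens its drug-related risks with effects on immune cells: "Moreover, SYK is implicated in the development and function of both T cells and B cells". For monitoring it states: "Safety laboratory contains WBC, differential blood count, and C-Reactive Protein".

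**The scale of measurement.** In Protocol Table 5.2.3: 1 the differential is headed "Automatic WBC differential, (relative" and the subset panel "Lymphocyte differentiation (relative", with no absolute scale for either. Reticulocytes in the same table are requested on both scales: "Reticulocytes (relative and absolute". Total white cells are a separate haematology test, not marked relative ("White Blood Cells (WBC) Platelet Count/Thrombocytes (quant"), in laboratory sets A, B and C. The differential is also in all three sets. The subsets are in A and C only.

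**The analysis.** Protocol 7.3.4 plans a comparison of laboratory values with reference ranges and adds: "Additionally, differences from baseline will be evaluated". SAP 7.8.2 says: "Laboratory data will be analysed qualitatively via comparison of laboratory data to their reference ranges". It flags values outside the range or defined as possibly clinically significant, and refers to an internal laboratory standard. It does not mention change from baseline.

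**The early stop.** SAP section 4 explains that the study ended after the 25 mg group and that several variables, including laboratory data, vital signs and ECG, get listings without descriptive analysis. SAP 6.1 gives 2 subjects on placebo and 6 on 25 mg. SAP 7.8.3 nevertheless includes change from baseline in the vital-signs listings.

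**The concern.** Two choices combine. First, a percentage is a weak scale for a fall in cell number. The share of each lymphocyte subset and the CD4:CD8 ratio stay the same when all lymphocytes fall in proportion, and the lymphocyte share of white cells falls by less than the count does. Second, a reference-range flag responds only when a value crosses a limit. It ignores a large within-subject shift that stays inside the range. The protocol's baseline comparison would have covered the second weakness, and the SAP does not carry it over.

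At stake is how clearly the report can speak to a risk that the protocol itself names. With 6 active and 2 placebo subjects, within-subject change is the most informative view of the data. As written, a reader would have to multiply WBC by the differential percentage, and again by the subset percentage, then compare visits by hand.

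**Working it through.** **1. Is the missing comparison explained by the early stop?**

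| Item | Laboratory data | Vital signs |
|---|---|---|
| Protocol 7.3.4 | Reference ranges, plus differences from baseline | On-treatment changes from baseline |
| SAP section 4 | Listings, no descriptive analysis | Listings, no descriptive analysis |
| SAP section 7.8 | 7.8.2: range and possibly-significant flags; no change from baseline named | 7.8.3: listings with change from baseline |

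The same sentence of SAP section 4 covers both, yet only vital signs keep the comparison. A listings-only report is therefore compatible with showing change from baseline. SAP 6.7 defines baseline generally as the last measurement before dosing, so a laboratory baseline exists.

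**2. What moves when lymphocytes fall?**

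The plan states no figure to reproduce. All baselines and limits below are assumptions, since reference ranges are held in the investigator site file. I also assume that subset percentages are taken out of lymphocytes, as the table does not state the denominator.

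Let W be baseline WBC, p the lymphocyte fraction and f the proportional fall in lymphocytes, other white cells unchanged.

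- New WBC = W(1 - pf)
- New lymphocyte fraction = p(1 - f)/(1 - pf)
- Subset percentages and CD4:CD8 ratio: unchanged if every subset falls by f

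With W = 6.0 x10^9/L, p = 0.33, f = 0.40:

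- Absolute lymphocytes: 6.0 x 0.33 = 1.98, falling to 1.98 x 0.60 = 1.19 (-40%)
- WBC: 6.0 x (1 - 0.132) = 5.21 (-13.2%)
- Lymphocyte percentage: 0.198/0.868 = 22.8%
- Subset percentages: no change

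For p from 0.25 to 0.40 and the same 40% fall, the lymphocyte percentage ends between 16.7% and 28.6% and WBC between 5.40 and 5.04.

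**3. How large a fall raises no flag on lymphocyte percentage?**

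Setting the new fraction equal to a lower limit L gives f = (p - L)/[p(1 - L)]. For p = 0.33 and L = 0.20, f = 0.13/(0.33 x 0.80) = 0.49.

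| Baseline lymphocytes | L = 18% | L = 20% | L = 25% |
|---|---|---|---|
| 28% | 44% | 36% | 14% |
| 33% | 55% | 49% | 32% |
| 40% | 67% | 62% | 50% |

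From W = 6.0, WBC ends between 4.4 and 5.8 across these cells. Whether WBC itself would be flagged at the lower end is unknown.

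**4. What if all white cells fall together?**

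A 40% fall takes WBC from 6.0 to 3.60 with every percentage unchanged. Here the WBC count carries the whole signal, so no common fall is hidden from every recorded variable.

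**5. Can absolute counts be derived?**

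Yes. WBC and the differential are in every set, so differential counts are available at all scheduled laboratory times. Subset counts need set A or C: by the Flow Chart, screening, Day 1 pre-dose, 24 h, Day 8 and end of trial. They are not available at the set B times (Day -1, 4 h and 48 h).

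**The case against.** A reader might infer that immune-cell safety is recorded only as percentages and that a uniform lymphocyte fall could go unreported. The documents do not support that. Total WBC is measured in sets A, B and C, and SAP section 7 lists every individual value. In the example the listing would show 33% becoming 22.8% and WBC 6.0 becoming 5.2. The supportable claim is that a within-range fall may be unflagged and not displayed as a change.

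Other points against:

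- SAP 7.8.2 has a second flag, for possibly clinically significant values, and findings the investigator judges clinically relevant become adverse events. This stands, though the criteria for that flag are not given.
- The internal laboratory standard is not available and might supply baseline columns or derived counts. This cannot be excluded. But the SAP spells out change from baseline for vital signs, so its silence here should be resolved in the text.
- SAP section 4 discloses the reduction to listings. It does, but it does not say that the protocol's laboratory baseline comparison is dropped.
- Protocol 1.4.2 expects the immune risk to be minimal and effects transient, and reports no relevant findings after single doses up to 70 mg in the earlier healthy-volunteer trial. This lowers the stakes. It does not close the gap between protocol and SAP.
- The example needs an equal fall across T, B and NK cells; a selective fall would move the subset percentages. Nothing in the documents predicts a uniform fall, so they give no ground for saying that the safety conclusion would be wrong.
- Eight subjects' listings can be read by hand. True, and it limits the impact.

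**Conclusion.** The point holds in a limited form. There is a real gap between protocol and SAP: the promised laboratory comparison with baseline is absent from SAP 7.8.2, is not declared dropped in section 4, and is kept for vital signs under the same listings-only decision. Because the differential and subsets are specified only as percentages, the flags that remain sit on a scale that understates a lymphocyte fall or, for subsets falling in proportion, does not register it.

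The size cannot be fixed from the documents. Under the assumed baselines (28% to 40%) and lower limits (18% to 25%), falls of 14% to 67% would raise no flag on lymphocyte percentage. These figures show the mechanism and do not predict an effect. With 8 subjects at one active dose level and all values listed, the impact is modest. The change is still worth making: it restores a comparison the protocol promised and uses data already collected.

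**What to change.** Change SAP 7.8.2 only:

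1. Derive absolute differential counts (WBC x relative differential) at all laboratory times.
2. Derive absolute subset counts (absolute lymphocytes x relative subset) at set A and C times: screening, Day 1 pre-dose, 24 h, Day 8 and end of trial. Confirm with the laboratory that lymphocytes are the denominator of the subset percentages.
3. List laboratory values, including these counts, with change from the SAP 6.7 baseline, by treatment and planned time.

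If the comparison has been dropped on purpose, say so in SAP section 4 and give the reason.

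No edit to Protocol Table 5.2.3: 1 is needed, and no new sample or assay. The cost is about ten derived variables and a slightly longer listing. A derived count carries the measurement error of each factor, so small changes should be read with that in mind.
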